20.2 A. How long will the data be stored?

The researchers will keep paper documentation (if any) and de-identified data for five years until we complete other associated studies. The expired, signed consent forms and materials will be deposited with the UB repository, whose security policy has been written according to best practice. All electronic data will be de-identified and stored on a secure, password-protected cloud.

20.3 A. Who will have access to the data?

Only the PI and other research team members will have access to both paper documentation and the cloud data.

20.4 A. Who is responsible for the receipt or transmission of the data?

The PI and other research team members are responsible for the receipt and transmission of the data.

20.5 A. How will the data be transported?

We will transport the data since it will be stored on a secure, password-protected cloud.

B. Confidentiality of Study Specimens

Describe the local procedures for maintenance of confidentiality of study specimens.

N/A: No specimens will be collected or analyzed in this research.
(Skip to Section 21.0)

20.6 B. Where and how will all specimens be stored? Include information about: physical controls, authorization of access, and labeling of specimens, as applicable.

Response: NOT APPLICABLE

20.7 B. How long will the specimens be stored?

Response: NOT APPLICABLE

20.8 B. Who will have access to the specimens?

Response: NOT APPLICABLE

20.9 B. Who is responsible for receipt or transmission of the specimens?

Response: NOT APPLICABLE

20.10 B. How will the specimens be transported?

Response: NOT APPLICABLE

21.0 Provisions to Monitor the Data to Ensure the Safety of Subjects*

N/A: This study is not enrolling subjects, or is limited to records review procedures only. This section does not apply.

NOTE: Minimal risk studies may be required to monitor subject safety if the research procedures include procedures that present unique risks to subjects that require monitoring. Some examples include: exercising to exertion, or instruments that elicit suicidality or substance abuse behavior. In such cases, N/A is not an acceptable response.

21.1 Describe the plan to periodically evaluate the data collected regarding both harms and benefits to determine whether subjects remain safe.

The PI will be responsible for safeguarding data integrity and safety monitoring for human subjects and communicating any negative outcomes or serious events to the IRB and other applicable offices/agencies.

The research team will meet weekly to review participant data and accrual. If participant accrual or retention drop under the requirement to complete the study, the PI and research team will discuss and develop strategies to overcome the identified issues. Record from the participants enrolled during each will be reviewed to ensure that all participants are eligible for the study. The research team will also monitor developments in the literature and results of related studies that may impact the participants or the ethics of the research.

21.2 Describe what data are reviewed, including safety data, untoward events, and efficacy data.

To ensure the integrity of the research study, we will review progress relevant to study recruitment and enrollment, intervention fidelity, clinical outcomes, and safety data. With the minimal to low risk associated with this research, there are no anticipated life-threatening adverse events for this proposed research project. In the rare occurrence, it will be reported to the PI and research team immediately. Researchers will notify the IRB within seven days of the adverse event occurrence. A thorough investigation will be initiated, including a review of the protocol to ensure no undue exposure to risk occurred.

21.3 Describe any safety endpoints.

There is a potential risk of emotional distress to participants when answering survey questions about symptoms or feelings. Although unlikely, participants may experience sensations of anxiety, depression, and worse physical symptoms. Participants will be instructed to rest and re-focus their attention from completing the survey in such a scenario. Suppose a participant expresses any distress, or the research team suspects the participant is experiencing distress for any reason during the research. In that case, the participant may be removed from the study and offered a referral to mental health services. The adverse events will be reported to the IRB by the PI within the required timeframe.

21.4 Describe how the safety information will be collected (e.g., with case report forms, at study visits, by telephone calls with participants).

The PI will collect safety data during telephone calls with the participant(s) and during data collection from the participant's self-evaluations.

21.5 Describe the frequency of safety data collection.

Safety data collection occurs once every two weeks for eight weeks and one hour during the focus group interview.

21.6 Describe who will review the safety data.

The PI and research team will review the safety data.

21.7 Describe the frequency or periodicity of review of cumulative safety data.

The review of cumulative safety data will occur weekly.

21.8 Describe the statistical tests for analyzing the safety data to determine whether harm is occurring.

We will use descriptive statistics (counts of the event) to determine the events of distress.

21.9 Describe any conditions that trigger an immediate suspension of the research.

We do not anticipate any situation that would trigger an immediate suspension of the study.

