22.0 Withdrawal of Subjects*

N/A: This study is not enrolling subjects. This section does not apply.

22.1 Describe anticipated circumstances under which subjects may be withdrawn from the research without their consent.

Participants may be withdrawn from the research without their consent if the PI or research team member discovers a participant is in severe psychological distress or is admitted into the hospital for a psychiatric condition.

22.2 Describe any procedures for orderly termination.

NOTE: Examples may include return of study drug, exit interview with clinician. Include whether additional follow up is recommended for safety reasons for physical or emotional health.

NOT APPLICABLE

22.3 Describe procedures that will be followed when subjects withdraw from the research, including retention of already collected data, and partial withdrawal from procedures with continued data collection, as applicable.

We will attempt to use all the available data obtained from all participants (intention to treat). Pre and post comparison of the experimental Group will be conducted as aggregate means using all available data collected.

When participants decide to leave the study, we will ask them if they would allow us to use the data we have collected before their decision to withdraw. If the subjects agree to use the data, the collected data will be handled and analyzed the same as research data. If the participants do not allow the use of the data, we will make every attempt to destroy the data.

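### Removing a distressed participant from the study, rather than only from MMPH, can tilt the section 22.3 pre-post comparison of PHQ-9 toward benefit

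*Combined protocol and SAP*

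**What the plan says.** Section 21.3 sets a broad trigger: "Suppose a participant expresses any distress, or the research team suspects the participant is experiencing distress for any reason during the research". The permitted response is "In that case, the participant may be removed from the study and offered a referral to mental health services". The wording concerns the study, not MMPH practice. Section 22.1 allows withdrawal from the research without consent when the team finds that "a participant is in severe psychological distress or is admitted into the hospital for a psychiatric condition".

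The template prompt for section 22.3 asks about "partial withdrawal from procedures with continued data collection, as applicable". The response deals only with data already collected. It promises to use what is available from everyone, under an intention-to-treat label, and states: "Pre and post comparison of the experimental Group will be conducted as aggregate means using all available data collected". It adds that people who decide to leave will be asked whether their earlier data may be used, and that the team will try to destroy the data if they refuse. Section 22.2, on orderly termination, is marked not applicable. Section 19.3 provides for chasing missing entries but does not mention people who have been removed.

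Table 1 (section 12.1) schedules PHQ-9, PAHSS and EmPHasis-10 at baseline, week 4 and week 8. Depression is in Aim 2 and Hypothesis 2. The endpoints in section 3.1 are PAHSS and EmPHasis-10, not PHQ-9. Section 19.1 names paired t-tests, repeated-measures ANOVA and a mixed model.

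**The concern.** The removal trigger is distress, and PHQ-9 is the scheduled questionnaire closest to distress. A person removed before week 8 has no week 8 score. If their baseline is kept, they count in the pre mean and not in the post mean. Because they are likely to be among the worse scorers, the post mean falls without anyone having improved.

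Hypothesis 2 predicts less depression, fewer PH symptoms and better quality of life at program end. A pilot of this size may be read mainly for its effect sizes, and a Cohen's d built on those two means would carry the same shift. The intention-to-treat label does not help, because it cannot supply a score that was never collected.

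**Working it through.** **Inputs from the protocol.** Section 5.1 plans 20 enrolled and at least 16 analysed, 8 to 10 per group. That reproduces: 16 / (1 − 0.20) = 20. The protocol gives no SD, between-visit correlation or removal rate, so the rest are assumptions.

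**Assumptions.** Normal scores in SD units, higher = worse; no true change; equal correlation rho = 0.5 to 0.7 between visits; one or two MMPH participants removed; their earlier data kept.

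**Step 1: effect of removing the highest scorers.** The expected highest and second-highest of n standard normal values are 1.539 and 1.001 for n = 10, and 1.424 and 0.852 for n = 8. The mean of those remaining, on the score used for selection, falls by:

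- n = 10: 1.539/9 = 0.171 (one removed); 2.540/8 = 0.318 (two)
- n = 8: 1.424/7 = 0.203 (one removed); 2.276/6 = 0.379 (two)

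**Step 2: the 22.3 aggregate comparison, removal following the week 4 score.** The pre mean keeps everyone, and the week 8 mean falls by rho × shift.

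| Group size | Removed | rho 0.5 | rho 0.7 |
|---|---|---|---|
| 10 | 1 | 0.086 | 0.120 |
| 10 | 2 | 0.159 | 0.222 |
| 8 | 1 | 0.102 | 0.142 |
| 8 | 2 | 0.190 | 0.266 |

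All entries are SD toward benefit. Simulation with 10 per group agrees. At an assumed PHQ-9 SD of 5 points, one removal is about 0.4 to 0.7 points. If correlation instead decays with time (0.5 to 0.7 over eight weeks), one removal from 10 gives 0.12 to 0.14 SD.

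**Step 3: looser link between trigger and outcome.** With correlation c between what prompts removal and the outcome, the shift is rho × c × the step 1 value. At c = 0.5, one removal gives 0.5 × 0.086 = 0.043 to 0.5 × 0.142 = 0.071 SD. This applies to PAHSS and EmPHasis-10, and to PHQ-9 if staff-noticed distress tracks it only partly.

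**Step 4: the 19.1 analyses, one removed from 10.**

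| Removal follows | Aggregate | Paired change | Mixed model |
|---|---|---|---|
| Week 4 score | 0.09 to 0.12 benefit | 0.00 | 0.00 |
| Baseline score, weeks 4 and 8 lost | 0.09 to 0.12 benefit | 0.05 to 0.09 against benefit | 0.00 |
| Unrecorded distress near week 6 | 0.09 to 0.12 benefit | 0.00 | 0.02 to 0.03 benefit |
| Would-be week 8 score (upper limit) | 0.17 benefit | 0.05 to 0.09 benefit | 0.07 to 0.11 benefit |

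At the upper limit the paired value is (1 − rho) × 0.171. The mixed value is (1 − 2 rho²/(1 + rho)) × 0.171, that is 0.667 × 0.171 = 0.114 at rho 0.5 and 0.424 × 0.171 = 0.072 at rho 0.7. With decaying correlation, the week 6 case gives 0.03 to 0.04 SD toward benefit for both paired and mixed.

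**Scale.** The standard error of a paired change with 10 people is sqrt(2(1 − rho)/10) = 0.32 SD at rho 0.5 and 0.24 SD at rho 0.7.

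**The case against.** The strongest reply is that section 19.1 is the analysis plan, and its within-person methods show no bias in the main case. The sentence in 22.3 sits in an answer about withdrawals, names no test, and may mean only that group means will be reported. That stands, and it limits the point to the aggregate comparison. But 22.3 is the section that deals with people who leave, and nothing says that 19.1 overrides it. The 19.1 methods also keep a smaller bias when distress develops after the last recorded score.

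The event may never happen. Section 21.3 says "Although unlikely, participants may experience sensations of anxiety, depression, and worse physical symptoms", and removal is discretionary. The step 2 figures also assume that the person removed is exactly the top scorer, and nothing ties removal to a PHQ-9 score. Both objections stand. So does the data rule: a voluntary leaver may refuse use of their data, and then the baseline goes too and the mismatch does not arise. Read with 22.1, removal for milder distress may need the participant's agreement and so come under that rule.

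Three stronger readings are tempting, and the documents do not support them:

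- *Removal hides harm.* Section 21.8 says "We will use descriptive statistics (counts of the event) to determine the events of distress", so the events remain on record.
- *All results tilt toward benefit.* The before-and-after change at each daily module use carries its own pair of ratings, so it escapes the mismatch, although averages over sessions can shift when later sessions are lost. A between-group contrast at week 8 moves toward benefit if only MMPH loses someone, against it if only the waitlist does, and by nothing if each loses one.
- *The listed endpoints are distorted to the same degree.* PAHSS and EmPHasis-10 are affected only as far as they correlate with distress.

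**Conclusion.** The point holds as a conditional and minor one. It needs a removal in the MMPH group before week 8, earlier data kept (removal by the team, or a leaver who permits use), and the 22.3 comparison carried out on unmatched means. Under the stated assumptions, the false improvement on an outcome that fully tracks distress is about 0.09 to 0.14 SD for one removal and 0.16 to 0.27 SD for two. It is about half that at a trigger-to-outcome correlation of 0.5, and zero with no removals. One removal shifts the estimate by less than its own standard error, but in a consistent direction. The documents do not show bias in the within-person analyses for the main case, and the paired test errs against benefit if removal follows baseline distress. The gap in the text is that stopping MMPH and stopping data collection are not separated.

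**What to change.** 1. In 21.3 and 22.1, make stopping MMPH the default response to distress. Still invite the person to the remaining week 4 and week 8 questionnaires, with their agreement and unless the questionnaires are the source of the distress. Keep full removal as a safety option.
2. In 22.3, replace the aggregate-mean comparison with the mixed model from 19.1, using baseline and week 4 data, or failing that the within-person change.
3. Report removals by group and reason.

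Section 11.1 says enrollment has ended, so item 1 helps only participants still in follow-up. Items 2 and 3 apply either way. The cost is wording in three sections and one withdrawal-reason field, since the analysis is already named. The downside is that a few people would answer questionnaires after stopping practice, and only if they agree.

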16.4 Describe your process to ensure that all persons assisting with the research are adequately informed about the protocol, the research procedures, and their duties and functions.

We will have at least monthly Research Team meetings to review participant recruitment, enrollment, research procedures, research-related issues. Team members will receive weekly updates about the overall progress of the study.

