28.4 Describe any process to ensure ongoing consent, defined as a subject's willingness to continue participation for the duration of the research study.

Emails will be sent to the participants each week by the research team to remind participants of their volunteer status and ability to withdraw from participation at any time.

28.5 Indicate whether you will be following "SOP: Informed Consent Process for Research (HRP-090)." Pay particular attention to Sections 5.4-5.9. If not, or if there are any exceptions or additional details to what is covered in the SOP, describe:

- *The role of the individuals listed in the application who are involved in the consent process*
- *The time that will be devoted to the consent discussion*
- *Steps that will be taken to minimize the possibility of coercion or undue influence*
- *Steps that will be taken to ensure the subjects' understanding*

We will be following HRP-900 with the exception that consent provisions will not be made to conduct consent in languages other than English even if this is preferred by the participant because we expect that the participants will speak English sufficiently to understand the consent form.

We have reviewed and will be following "SOP: Informed Consent Process for Research (HRP-090)."

Non-English Speaking Subjects

N/A: This study will not enroll Non-English speaking subjects.
(*Skip to Section 28.8*)

28.6 *Indicate which language(s) other than English are likely to be spoken/understood by your prospective study population or their legally authorized representatives.*

NOTE: The response to this Section should correspond with your response to Section 8.4 of this protocol.

Response:

NOT APPLICABLE

28.7 *If subjects who do not speak English will be enrolled, describe the process to ensure that the oral and written information provided to those subjects will be in that language, how you will ensure that subjects are provided with a sufficient period of time to consider taking part in the research study, and any process to ensure ongoing consent. Indicate the language that will be used by those obtaining consent.*

NOTE: Guidance is provided on "SOP: Informed Consent Process for Research (HRP-090)."

Response:

NOT APPLICABLE

Cognitively Impaired Adults

N/A: This study will not enroll cognitively impaired adults.
(*Skip to Section 28.9*)

28.8 *Describe the process to determine whether an individual is capable of consent.*

Response: NOT APPLICABLE

Adults Unable to Consent

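### Two-weekly safety data collection does not fit a seven-day IRB notice counted from occurrence, nor a weekly safety review

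*Combined protocol and SAP*

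**What the plan says.** Section 21.0 of the protocol sets three intervals.

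- **Collection (21.5):** "Safety data collection occurs once every two weeks for eight weeks", with the interview as a further occasion.
- **Review (21.7):** "The review of cumulative safety data will occur weekly". Section 21.1 matches this: "The research team will meet weekly to review participant data and accrual".
- **Notice (21.2):** "Researchers will notify the IRB within seven days of the adverse event occurrence". The clock starts when the event happens, not when the team hears of it.

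Section 21.4 names the sources: "The PI will collect safety data during telephone calls with the participant(s) and during data collection from the participant's self-evaluations".

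Two further statements bear on scope. In 21.2 the seven-day sentence comes directly after text saying that life-threatening events are not expected and that any such event would reach the PI and team at once. Section 21.3, on distress and worsening symptoms, promises IRB reporting by the PI to a deadline that it does not express in days.

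**The concern.** A reporting deadline counted from occurrence can be met only if the team learns of events inside it. Here the scheduled interval for asking is twice the time allowed for reporting, and twice the review interval.

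Participants practise at home (14.1), and medical records are not consulted (12.4, 18.2), so the team depends largely on what participants tell it. If an event is not volunteered, the next scheduled collection is where it comes to light.

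Timely discovery matters because other parts of the plan rely on it. Withdrawal without consent under 22.1 depends on the team finding out about severe distress or a psychiatric admission, and 21.9 foresees no situation that would suspend the study. Collection, review and IRB notice therefore carry most of the oversight.

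**Working it through.** The plan gives no figure of its own to reproduce. The check is interval arithmetic.

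**Inputs**
- Collection interval T = 14 days (21.5).
- Notice limit D = 7 days from occurrence (21.2).
- Review interval = 7 days (21.7).
- Programme length = 8 weeks = 56 days (21.5).

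**Step 1: collections against reviews.** 56/14 = 4 scheduled collections; 56/7 = 8 reviews. Every second review has no new scheduled collection to look at.

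**Step 2: worst case.** The longest delay from event to scheduled collection is T = 14 days. The overrun is T − D = 14 − 7 = 7 days. This needs no assumption about when events occur.

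**Step 3: share past the limit.** Assume that event times are uniform over the interval, that nothing signals the event earlier, and that the seven-day limit applies to it. Mean delay = T/2 = 7 days. Share older than D at collection = (T − D)/T = 7/14 = 0.50.

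**Step 4: lag to review.** If the team takes in the information only at a review L days after collection, the longest delay is T + L and the share past day 7 is (T + L − D)/T. The same formulas with T = 7 show what weekly collection would do.

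| L (days) | T = 14: longest delay | T = 14: share past day 7 | T = 7: longest delay | T = 7: share past day 7 |
|---|---|---|---|---|
| 0 | 14 | 0.50 | 7 | 0 |
| 1 | 15 | 8/14 = 0.571 | 8 | 1/7 = 0.143 |
| 3 | 17 | 10/14 = 0.714 | 10 | 3/7 = 0.429 |
| 7 | 21 | 14/14 = 1 | 14 | 7/7 = 1 |

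Weekly collection removes the overrun only if replies are read on the day they arrive. In the worst case it leaves no slack against a clock that runs from occurrence. If the clock ran from the team's awareness, the deadline conflict would disappear at any collection interval, but late discovery would remain.

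**Step 5: other described contacts.** None asks about adverse events.
- The coordinator's weekly check (19.3) is for survey completion and missing data.
- The weekly email (28.4) reminds participants that taking part is voluntary.
- The Table 1 reminder has no stated safety content, and the table has no safety row.
- The app ratings cover pain, anxiety, fatigue and dyspnea around module use, and no section assigns anyone to screen them for safety.

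**The case against.** The strongest reply concerns scope. In context the seven-day sentence most naturally governs the rare life-threatening event, which also has an immediate reporting route. Distress and worsening symptoms come under 21.3, which states no number of days. This stands: for those events the documents do not show that a seven-day limit is breached. It does not close the gap, because the immediate route names neither a reporter nor a channel for a participant at home, and 21.3 leaves its deadline undefined.

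Second, participant data do reach the team between collections. Section 21.4 could count the daily ratings as self-evaluations, the coordinator contacts participants about missing entries, and 23.2 has weekly meetings that consider safety concerns. A participant admitted to hospital might stop making entries and be noticed that way. This also stands in part: the alternate reviews lack a scheduled safety collection, but they are not empty of all data. None of these routes is an adverse-event question.

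Third, participant-facing consent text was not available for this review and may ask participants to report problems. That cannot be checked here.

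Two stronger readings are tempting, and the documents support neither. A reader might infer that the IRB deadline is bound to be missed. It is not: an event may be volunteered, seen in the ratings, or fall in the second week before a collection. A reader might also see a contradiction between the weekly meetings in 21.1 and section 16.4, which says "We will have at least monthly Research Team meetings". Weekly meetings satisfy that wording, and 16.4 concerns keeping staff informed.

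**Conclusion.** The conflict is real and limited. Following 21.5 exactly, an event found only at scheduled collection can be up to 14 days old, 7 days past the limit in 21.2 wherever that limit applies, and four of the eight weekly reviews have no new scheduled collection.

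The one-half share is conditional on uniform timing, no earlier signal, and the seven-day limit applying to the event. Spontaneous reports, the immediate route or the app ratings would lower it by an amount that the documents do not allow one to estimate. They give no event rate, so no number of late reports follows for the 20 participants.

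The protocol describes the study as minimal to low risk, which keeps the point modest. It should still be corrected, because the plan's own commitment can fail when its own schedule is followed.

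**What to change.** 1. Reconcile 21.2, 21.3, 21.5 and 21.7. State which events the seven days cover, what deadline applies to the rest, and whether the clock runs from occurrence or from the team's awareness. Record both dates, subject to the IRB's own requirement.
2. Add one adverse-event question to a weekly contact already planned. Section 28.4 offers one: "Emails will be sent to the participants each week by the research team". The weekly Table 1 reminder is another. Collection would then be at least as frequent as the weekly review. If the clock stays at occurrence, have replies read on arrival, since weekly collection alone leaves no slack.
3. In the same message, ask participants to report events between contacts and say to whom.

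The cost is protocol wording, one question, and a few more replies for the coordinator to read. It needs no extra visit or staff. Section 11.1 says enrolment has ended, so the change helps only participants still active.

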23.0 Risks to Subjects*

23.1 List the reasonably foreseeable risks, discomforts, hazards, or inconveniences to the subjects related to their participation in the research. Consider physical, psychological, social, legal, and economic risks. Include a description of the probability, magnitude, duration, and reversibility of the risks.

NOTE: Breach of confidentiality is always a risk for identifiable subject data.

There are no foreseeable physical risks, discomfort, hazard, or inconveniences to the subjects related to their participation in this research. However, there is potential physical harm if participants use the M-App in circumstances that require total attention, such as driving or operating heavy machinery. There is an inherent risk of participants becoming so relaxed and drift off into a sleep state, which may put them in danger during these activities. Therefore, we will instruct participants in the proper use of the M-App and the environment/conditions they need to avoid practicing with the M-App.

For a Zoom intervention group, there is always the chance that someone will share something someone else said (confidentiality breach). At the beginning of the interview, we will remind participants not to share this information with anyone. (This information will be a part of the consent document, indicating no guarantee that this may not occur).

There is a potential risk of emotional discomfort to participants when answering survey questions about symptoms or feelings. Although unlikely, participants may experience sensations of anxiety, depression, and worse physical symptoms. Participants will be instructed to rest and re-focus their attention from completing the survey in such a scenario. If needed, participants will be given the contact information in their local areas (according to their primary care doctors). Questionnaires included in this research study are standardized tools used widely with no reported adverse harm. Fatigue is possible when answering questions from a battery of questionnaires. However, most surveys used in this study are shortened versions that generally require less than 10 minutes to complete.

23.2 Describe procedures performed to lessen the probability or magnitude of risks, including procedures being performed to monitor subjects for safety.

To address potential physical harm (mentioned above), we will provide specific instructions on how to complete the M-App modules at home.

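### The only planned harm analysis counts distress, so the physical harms that the protocol itself foresees have no planned count

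*Combined protocol and SAP*

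**What the plan says.** Section 23.1 begins: "There are no foreseeable physical risks, discomfort, hazard, or inconveniences to the subjects related to their participation in this research". The next sentence reads: "However, there is potential physical harm if participants use the M-App in circumstances that require total attention, such as driving or operating heavy machinery". It goes on to treat drifting into sleep as a risk inherent in the practice. Section 23.3, which asks for risks that cannot currently be foreseen, gives falling asleep as its one example. Section 23.2 answers the physical harm with instruction: "To address potential physical harm (mentioned above), we will provide specific instructions on how to complete the M-App modules at home".

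Section 21.3, on safety endpoints, concerns mainly emotional distress from answering survey questions. In that context it says: "Although unlikely, participants may experience sensations of anxiety, depression, and worse physical symptoms". The responses it gives are rest, possible removal from the study and referral to mental health services.

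Section 21.8 asks how safety data will be analysed to find out whether harm is occurring. The full answer is: "We will use descriptive statistics (counts of the event) to determine the events of distress".

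Other provisions are wider. Section 21.1 has the PI communicate negative outcomes and serious events to the IRB. Section 21.2 includes safety data in the review. Section 21.3 sends adverse events to the IRB. Section 21.4 takes safety data from telephone calls and participants' self-evaluations. Section 21.5 sets collection at every two weeks for eight weeks, plus the focus group interview.

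**The concern.** The plan names physical harms in one place and leaves them out of the harm tally in another. If 21.8 is followed as written, the safety table will show distress events and nothing else. A reader who sees few or none could take that as a statement about harm in general, when the analysis never covered an injury during drowsy App use.

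This matters somewhat more because staff will not see most of the practice. Under 6.1 each session includes gentle body movement and a restorative pose, and six of the eight weekly sessions are recorded videos. Table 1 adds self-guided practice of 20 minutes on six days a week. What is asked at the safety contact, and what is then tallied, is the main route by which a physical event would enter the results.

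**Working it through.** The documents state no safety rate, threshold or precision figure, so there is none to reproduce. The check has two parts.

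**Step 1. Compare what is foreseen, collected, reported and counted.**

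| Harm | Foreseen | Collected | Reported | Planned count |
|---|---|---|---|---|
| Emotional distress | 21.3, 23.1 | 21.4, general terms | 21.3, to the IRB | 21.8 |
| Worse physical symptoms (from answering surveys) | 21.3, 23.1 | 21.4, general terms | 21.3, general terms | None |
| Physical harm from drifting to sleep during App use | 23.1; listed as unforeseeable in 23.3 | 21.4, general terms | 21.1 to 21.3, general terms | None |

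The gap is in the last column. No section defines a physical adverse event, gives event categories or plans a table of such events. It is unlikely that distress in 21.8 was meant to include physical events: 21.3 introduces the term as emotional distress and pairs it with mental health referral, and the withdrawal criteria in 22.1 are psychological or psychiatric only.

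Table 1 has pain, anxiety, fatigue and dyspnea rated before and after daily module use. Section 19.1 analyses the effect of App use with paired t-tests and repeated-measures ANOVA, that is, as outcome comparisons. Nothing turns an individual worsening into a safety event, and the ratings cannot record an injury.

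**Step 2. What a complete count could show.**

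With zero events in n exposed participants, the exact one-sided 95% upper limit for the event rate is 1 − 0.05^(1/n).

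The values of n come from 5.1: 20 enrolled, at least 16 for the aims, 8 to 10 per group. How many are exposed to MMPH is an assumption. Section 5.1 has waitlisted controls, while 12.1 says that enrolled participants receive the eight-week intervention.

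| Assumption | n | Calculation | Upper limit |
|---|---|---|---|
| One group exposed, low end | 8 | 1 − 0.05^(1/8) | 31.2% |
| One group exposed, high end | 10 | 1 − 0.05^(1/10) | 25.9% |
| All exposed in time, minimum retained | 16 | 1 − 0.05^(1/16) | 17.1% |
| All exposed in time, full enrolment | 20 | 1 − 0.05^(1/20) | 13.9% |

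These limits apply only to event types that are actually asked about and counted. They show how little reassurance even a full count could give; they do not measure the size of the gap in 21.8.

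**The case against.** The strongest reply is that nothing is lost. Collection under 21.4 is not restricted to distress, 21.1 to 21.3 report adverse events to the IRB, and 19.1 promises frequency distributions for all variables. A reader might infer that physical harms would go unrecorded or unreported; the documents do not support that. What remains is that case reporting is not a planned count, and that 19.1 can tabulate a physical event only if a variable for it exists. None is defined.

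A reader might also infer that the protocol foresees breathlessness brought on by the body-movement exercises and then ignores it. It does not name that harm. The phrase about worse physical symptoms follows the risk of answering survey questions, and dyspnea is rated before and after daily module use. The physical harm that the protocol ties to the intervention itself is falling asleep when full attention is needed.

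The two sentences of 23.1 can be read as a general statement followed by an exception. That softens the contradiction but does not remove it: a risk described as inherent cannot also be unforeseeable, and 23.3 repeats the misclassification.

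Two practical objections stand. Events during App use should not occur while a participant is waitlisted, so comparing them between groups would tell nothing. And 11.1 says that enrolment has ended, so a new question may reach few people. Finally, the aims in 2.1 cover feasibility, acceptability and symptom impact. There is no safety aim, and no section plans a no-harm claim.

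**Conclusion.** The point holds in a limited form. Sections 21.3 and 23.1 foresee physical harms, 21.8 plans a count of distress only, and so physical adverse events have no planned count. Sections 23.1 and 23.3 also disagree on whether the sleep-related risk is foreseeable.

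The effect on the trial's conclusions is modest. The safety analysis is descriptive in any case, and zero events would exclude only rates above about 26% to 31% with 10 to 8 exposed participants, or about 14% to 17% with 20 to 16. Which range applies depends on whether waitlisted participants later receive MMPH. Importance is minor to moderate for a 20-person pilot that the protocol describes as minimal to low risk.

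**What to change.** 1. In 23.1, reconcile the first two sentences. In 23.3, stop listing falling asleep as unforeseeable when 23.1 foresees it.
2. In 21.3, name the physical events to be recorded: injury or near-injury during App use, and worsening physical symptoms during or after a session.
3. At the existing two-weekly contact (21.5), add one question on these events for participants still being followed. For those who have finished, use the safety records already held and say that the question was not asked systematically.
4. In 21.8, replace the distress-only count with counts of all adverse events by type, among participants while exposed to MMPH, with exact confidence limits and the number exposed. Show waitlist-period events separately, only for event types that can occur without the App, and state whether waitlisted participants receive the safety contacts.

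This is a cheap improvement. It costs a slightly longer call and one more table, and needs no change to the sample size or the outcome analyses.
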